***Scores**

Sinuses: 0= no mucosal thickening, 1= partial opacification, 2= total opacification

OMC: 0= not occluded, 2=obstructed

CT evidence of inflammation of the sinuses will be defined as mucosal thickening of at least one paranasal sinus and does not have to be severe enough to be classified as “partial opacification” or have a Lund and MacKay score of 1 or greater.

Data Collection

Sources of Research Material: All research-related information, including responses to the selected patient-reported outcome measures, will be captured electronically.. Week 2, Week 4, and Week 6 patient-reported outcome measures will be captured via an email sent to subjects with direct linkage to REDCap™ (Research Electronic Data Capture). All data will be stored in a specially designed database created by staff in the Clinical Outcomes Research Office using REDCap™. Patient confidentiality will be maintained through the use of unique patient ID.

Assessment of Treatment Efficacy: The change in the average SNOT-22 scores between baseline and eight weeks will serve as the primary outcome measure in this study and will be calculated as:

$$\text{Primary Outcome Measure, } \Delta\text{SNOT-22} = \text{SNOT-22}_{\text{baseline}} - \text{SNOT-22}_{\text{8-week follow up}}$$

To assess the trajectory of change within subjects randomized to the two treatment arms the baseline, two-week, four-week, six-week, and eight-week SNOT-22 assessment will be compared.

Assessment of Treatment Safety: As described above, 10 participants from each study arm will be selected for a cosyntropin test to assess for effects of mometasone nasal irrigation on the HPA axis. Treatment safety will also be assessed by patient interview and will include collection of adverse events experienced by the patient during the eight-week participation.

Risk Assessment: Mometasone has a potent glucocorticoid activity and weak mineralocorticoid activity. As an inhaled product, mometasone has an onset of action in 24 hours and peak effect between 1-4 weeks. The drug is well-tolerated and the more frequent side effects include: nose irritation, epistaxis, lightheadedness, and upset stomach. At recommended daily doses in both pediatric and adult patients, no adverse effects were seen on the HPA axis.²⁹

To assess the time trajectory of change within subjects randomized to the two treatment arms, the baseline, 2 week, 4 week, 6 week, and 8 week SNOT-22 assessments will be computed and compared. Within group differences will be compared using a repeated measure ANOVA. A general linear model (GLM) approach will be used to explore through the testing of an interaction effect (treatment group x time) whether the magnitude and pattern of change in SNOT-22 scores at baseline, 2 weeks, 4 weeks, 6 weeks, and 8 weeks are different between the 2 treatment groups. In addition to allowing for exploration of the interaction effect, the GLM model allows for evaluation of estimated means after controlling for potential confounders. A robust regression model will be used if the assumption of the GLM model will not be met. The distribution of responses on the Clinical Global Impression (CGI) scale will be calculated within each intervention arm and the difference in responses between the two intervention arms will be compared for statistical significance with the chi-square statistic.

All statistical analyses will be performed with the appropriate statistical software e.g. SAS, SPSS. Statistical significance will be defined as a two-tailed test of significance p value of 0.05 or less.

Stopping rules based on the work of O'Brien and Fleming³⁸ for the conduct of clinical trials will be followed. An Intention-to-Treat analysis will be used for the final data analyses.

Sample Size Calculations: The sample size for this study was calculated based on achieving a difference of 9 points or more on SNOT-22 scores. Thus, to be able to detect with 80% power at the 2-sided alpha level of 0.05 a difference of 9 points or greater between the 2 treatment groups, a total of 50 subjects- 25 subjects per group- will be necessary. With an anticipated 15% drop out/non-compliance rate, the total sample size planned for this study will be 44 subjects.

Remuneration: Subjects will receive \$50 after baseline and \$50 at final visit and upon successful completion of trial.

For subjects who complete the coynstropin test, they will receive up to an additional \$100. Subjects will receive \$50 after the baseline cosyntropin test and another \$50 following the second cosyntropin test.

Timeline of the Study

Subjects will be enrolled in the study for a total of eight weeks. Given the volume of patients seen at the Adult Otolaryngology service with diagnosis of CRS, we anticipate it will take one year to complete enrollment.

Calendar of Events (Patient)

Study Activity	Baseline (Time 0)	Week 1	Weeks 2,4,6	Week 8
Consent	X			
Randomization	X			
SNOT-22	X		X	X
Cosyntropin test with blood draw	X			X
ACE-27 Comorbidity	X			
ENT Physical examination w/ Endoscopic examination*	X			X
Radiological Examinations (ex. CT sinus)*	X	X	X	X
Written instructions for administration of intervention	X			
Intervention - mometasone nasal irrigation or mometasone nasal spray		X	X	X
Global Clinical Impression	X	X	X	X
Questionnaire for Olfactory Dysfunction	X			X
Olfactory Dysfunction Outcomes Rating (ODOR)	X			X
UPSIT	X			X
Participant Stipend	X			X

* Results only from nasal endoscopic examination and radiological examination performed for clinical purposes during the study will be collected for research purposes.

Literature Citations

1. Rosenfeld RM, [name] JF, Chandrasekhar S et al. Clinical practice guideline (update): adult sinusitis. *Otolaryngology--head and neck surgery : official journal of American Academy of Otolaryngology-Head and Neck Surgery* 2015; 152:S1-s39.
6. Bhattacharyya N. Incremental health care utilization and expenditures for chronic rhinosinusitis in the United States. *The Annals of otology, rhinology, and laryngology* 2011; 120:423-427.

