The SNOT-22 (©2006, Washington University, St. Louis, MO) will be used to capture the physical, functional, and emotional consequences of rhinosinusitis. The SNOT-22 is a validated, patient-reported outcome measure applicable to chronic sinonasal conditions.³³ The severity of 22 rhinosinusitis-related symptoms and physical signs are measured using a Likert scale as follows: 0= "No problem"; 1="Very mild problem"; 2="Mild or slight problem"; 3="Moderate problem"; 4="Severe problem"; and 5="Problem as bad as it can be". Higher total scores on the SNOT-22 suggest worse patient functioning or symptom severity (score range: 0-110). A minimally clinically improved difference (MCID) in symptoms that is perceptible and pertinent to the individual patient on the SNOT-22 has been previously described as an improvement of at least 9 points.^{33,34}

Primary Outcome Measure

Study participants will be asked to complete the SNOT-22 at baseline, two weeks, four weeks, six weeks, and eight weeks following start of medications. The SNOT-22 score will be calculated as the average per item score for each of the 22 items and the value will range between 0 and 5. For subjects who answer less than 22 items (i.e., don't completely answer the SNOT-22), the total score will be the average per item value for the items that were answered. The change in SNOT-22 scores between baseline and eight weeks will serve as the primary outcome measure in this study and will be calculated as:

Primary Outcome Measure, $\Delta\text{SNOT-22} = \text{SNOT-22}_{\text{baseline}} - \text{SNOT-22}_{\text{8-week follow-up}}$.

To assess the trajectory of change within subjects randomized to the two treatment arms the baseline, two-week, four-week, six-week, and eight-week SNOT-22 assessment will be compared.

Secondary Outcome Measure.

University of Pennsylvania Smell Identification Test (UPSIT):

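### In their standard form, the five-visit SNOT-22 trajectory analyses drop any subject who misses one e-mailed form; a mixed model on all available scores would keep them

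*Combined protocol and SAP*

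**What the plan says.** The Statistical Analysis section has two trajectory analyses over the same five assessments: "the baseline, 2 week, 4 week, 6 week, and 8 week SNOT-22 assessments will be computed and compared". For change within each arm, "Within group differences will be compared using a repeated measure ANOVA". For the comparison of arms, "A general linear model (GLM) approach will be used to explore through the testing of an interaction effect (treatment group x time"). The second is worded as exploratory.

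The Data Collection section says how the middle three scores are obtained: "Week 2, Week 4, and Week 6 patient-reported outcome measures will be captured via an email sent to subjects". The two ends, baseline and week 8, are not part of that e-mail collection.

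Three other statements bear on what happens when a score is absent:

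- The Primary Outcome Measure section handles unanswered items within a form: "the total score will be the average per item value for the items that were answered". Nothing is said about a form that is missing altogether.
- The fallback model is tied to assumptions: "A robust regression model will be used if the assumption of the GLM model will not be met".
- The analysis set is named but not defined: "An Intention-to-Treat analysis will be used for the final data analyses".

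Software is given only by example ("All statistical analyses will be performed with the appropriate statistical software e.g. SAS, SPSS"), with no procedure or data layout named.

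**The concern.** Repeated-measures ANOVA, and the general linear model with repeated measures as usually run, take one row per subject holding all five scores. A row with a gap is discarded whole, including the scores that were collected. A subject could finish treatment, supply baseline and week-8 scores and count in the primary t-test, yet be absent from both trajectory analyses because of one unanswered e-mail.

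Two things are at stake. One is precision, in a trial of at most 50 subjects. The other is the comparison itself: those who answered every form are a group selected after randomisation. If answering depends on symptoms or on arm, the estimated difference in trajectory can be biased.

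**Working it through.** **1. Does anything in the plan prevent the deletion?** The item-level averaging rule needs a form with at least some answers. The robust-regression fallback is triggered by failed model assumptions, not by missing data. No imputation or mixed model is named. The intention-to-treat sentence states an aim, but the named methods do not deliver it when a form is missing. As a check, a standard repeated-measures ANOVA routine given 6 subjects by 5 times with one score removed refused to run because the data were unbalanced. In such a routine the subject must be dropped or the value filled in.

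**2. How many subjects?** The plan gives no figure for the trajectory analyses and no non-response rate, so there is nothing to reproduce. Let m be the probability of missing each e-mailed form, assumed independent across the three forms. Among subjects with both baseline and week-8 scores, the share kept is (1 − m)³.

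| m (assumed) | kept, (1 − m)³ | dropped | SE ratio, 1/√kept |
|---|---|---|---|
| 3% | 0.913 | 9% | 1.05 |
| 5% | 0.857 | 14% | 1.08 |
| 10% | 0.729 | 27% | 1.17 |

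The base is week-8 completers. If the whole of the plan's 15% drop-out/non-compliance allowance is taken as missing week-8 data, 50 × 0.85 = 42.5 subjects have both scores. The trajectory analyses then keep about 39, 36 or 31 of them. As shares of everyone randomised, the e-mail forms alone remove 0.85 × 0.087 = 7%, 0.85 × 0.143 = 12% or 0.85 × 0.271 = 23%.

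Independence is the unfavourable case. If the same people miss all three forms, the share dropped is simply m: 10% rather than 27% at m = 10%.

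**3. What does it cost in power?** The plan gives no SD. Its 25 per group, 80% power, two-sided 0.05 and 9-point difference imply 9 / [(1.960 + 0.842) × √(2/25)] = 11.36 for the SD of change (normal approximation). Simulations used 42 subjects, an assumed SD of 11.36 at each visit and a within-subject correlation of 0.5, which gives the same SD for change: 11.36 × √(2 × (1 − 0.5)) = 11.36. Forms were missing completely at random.

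- With a difference growing linearly to 9 points, the power of the group-by-time test was about 0.61 with every form returned. On complete cases it was about 0.53 at m = 5% and 0.45 at m = 10%.
- At m = 10%, across three shapes of the difference (linear growth; full by week 2; half at week 2, then full), power was 0.43 to 0.58 on complete cases and 0.58 to 0.73 using all available scores.

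**4. Which test replaces it?** The plan's interaction spans baseline, so it asks whether change from baseline differs by arm. If baseline is moved to the covariate side and only treatment by visit over weeks 2 to 8 is tested, the question changes to whether the arm difference varies among those weeks. An effect that is full by week 2 and then sustained falls into the treatment main effect. Under the assumptions above, that narrower test had only about 5% to 6% power for such an effect, even with no missing data. The Risk Assessment paragraph describes onset within 24 hours and a peak between 1 and 4 weeks, so an early plateau is plausible.

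**The case against.** The strongest reply is that the plan never says incomplete subjects are deleted. It names no procedure, and a linear model fitted to one row per score, with a subject term, keeps partial records: in a check with 100 scores, removing one left 99 in the fit. That stands, so deletion is an inference from the usual form of the named methods. But the plan does not specify such a fit, and repeated-measures ANOVA in particular is normally run on complete rows. The ambiguity itself needs settling before the data are seen.

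Second, the between-arm test is exploratory, and repeated-measures ANOVA is assigned only to the within-group comparison. Both are correct and limit the weight of the point.

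Third, the non-response rates are assumptions, and the plan is silent on reminders, so good return rates are possible. This also stands. At 3% per form the loss is modest.

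A reader might infer more than the documents support:

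- That the main efficacy result is at risk. It is not: the t-test and the responder comparison use only baseline and week 8.
- That 27% of all randomised subjects would be lost to e-mail gaps at m = 10%. That is the share of week-8 completers.
- That standard errors would rise 1.27-fold, from 1/√(0.85 × 0.729). That figure includes the 15% loss, which is a separate matter and partly non-compliance rather than missing data.

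**Conclusion.** The point holds as a gap in two supporting analyses. In their standard form the named methods would drop a subject for one missed e-mailed form, no stated rule prevents it, and the result does not fit an unqualified intention-to-treat commitment. For assumed independent non-response of 3%, 5% or 10% per form, about 9%, 14% or 27% of week-8 completers are dropped, and standard errors are up to about 1.05, 1.08 or 1.17 times those with complete forms. These are upper figures, because clustering of missed forms in the same people reduces them. A mixed model recovers part of the loss, not all of it, since the missing scores stay missing. Bias is possible but cannot be sized from the documents. No confirmatory conclusion depends on this, so it is a change worth making rather than a condition for the trial's validity.

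**What to change.** Replace both trajectory analyses with one likelihood-based linear mixed model for repeated measures, fitted to all available SNOT-22 scores of all randomised subjects:

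- Keep baseline as one of the five response times. Include treatment, visit and treatment by visit, with an unstructured within-subject covariance and a named simpler structure if that does not converge.
- Test treatment by visit over all five times. Take the within-arm changes from the same model.
- Alternatively, use baseline as a covariate and test treatment and treatment by visit jointly over weeks 2 to 8. In that version do not test treatment by visit alone.
- State that a missing form is not imputed and the subject's other scores are used.

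The cost is plan wording. SAS and SPSS, the packages the plan names as examples, both fit this model, and no new data, visits or subjects are needed. The downsides are a missing-at-random assumption, which is weaker than complete-case analysis generally needs, and the choice of a covariance structure in a small sample. The wording should be fixed before unblinded analysis.

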
Like budesonide, mometasone furoate is a second-generation INC. The newest of the INCS, mometasone is currently used as an inhalational drug for the treatment of asthma, allergic rhinitis, and nasal polyps. Due to its increased lipophilicity and extensive hepatic metabolism, however, mometasone has a markedly reduced systemic availability as compared to budesonide (<0.1% versus 34%, respectively).²⁸ Furthermore, using various pharmacologic tests, including competition and McKenzie assays, mometasone has been shown to have higher potency than budesonide.²⁸ While corticosteroids can suppress the HPA axis, multiple studies have demonstrated that INCS have no significant impact on the HPA axis. In 6 randomized controlled parallel-group or placebo trials in adults and children, no evidence of HPA axis suppression was seen.²⁹

In a recent double-blinded, placebo-controlled randomized clinical trial (RCT), Harvey et al demonstrated that MF nasal irrigation was superior to MF nasal spray in the management of CRS symptoms following sinus surgery, as measured by patient-reported outcomes and

endoscopic findings.²³ In the study, participants were assigned to either mometasone capsules (2 mg daily) or placebo intervention for 12 months following sinus surgery. The MF nasal irrigation group had a significantly greater improvement in nasal blockage visual analog symptoms compared to that of the MF nasal spray group ($p=0.029$). Furthermore, on endoscopic examination, the MF nasal irrigation group had significantly greater disease suppression than the MF nasal spray group, as evidenced by lower modified Lund-Kennedy endoscopic scores ($p=0.018$). Harvey et al reported no adverse effects from their dosage of mometasone.

Due to mometasone's favorable pharmacologic properties, we propose to evaluate the effectiveness of the addition of mometasone to large-volume, low-pressure sinus saline irrigation for patients with CRS without polyps in a single-site randomized clinical trial. We hypothesize that the addition of MF to a large-volume, low-pressure sinus saline irrigation will result in clinically meaningful benefits for patients with CRS as measured by subjective and objective outcome measures. We anticipate that MF dispensed in a large volume, low-pressure device will be superior to that of MF nasal spray combined with nasal saline irrigation in the medical management of CRS in surgery-naïve, non-polyp patients.

II. Specific Aims

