The UPSIT is a test of olfactory identification and consists of four 10-page booklets, with a total of 40 items. On each page, there is a different “scratch and sniff” strip and four choice options. Subjects are asked to scratch each strip with a pencil to release the scents, detect the smell, and identify the smell from the four choice options. The UPSIT comes from a scoring rubric that identifies the normalcy benchmark based on age and gender. The UPSIT is commercially available, takes 10-15 minutes to complete, and is the gold standard test to assess smell identification. Subjects will complete the UPSIT at their baseline and final visit.

Clinical Global Impression Scale (CGI):

The overall response to treatment will be measured with a modification of the Clinical Global Impression (CGI) scale.^{32,35} Upon completion of the study, subjects will be asked to answer the following question: "Overall, how would you rate your response to treatment?" Response options are: 1 = *Very Much Improved*, 2 = *Much Improved*, 3 = *Minimally Improved*, 4 = *No Change*, 5 = *Minimally Worse*, 6 = *Much Worse*, 7 = *Very Much Worse*. In addition, subjects will be asked to rate their subjective sense of smell pre- and post-intervention.

Questionnaire for Olfactory Dysfunction (QOD):

The QOD is a validated quality of life questionnaire for patients with olfactory disorders. Subjects will complete the QOD at their baseline and final visit.

Olfactory Dysfunction Outcomes Rating (ODOR):

The ODOR is a quality of life measure capturing physical, functional, and emotional limitations specific to smell loss. It is currently undergoing validation and is designed to be more concise, readable, and comprehensive than the QOD. Subjects will complete the ODOR questionnaire at their baseline and final visit.

Physical Examination including nasal endoscopy performed for clinical purposes The physical examinations will be done as part of routine care during the patients’ scheduled clinic visit. The findings from the endoscopic examination will be collected for research purposes and will be recorded using the grading system proposed by Lund and Kennedy.³⁶

Endoscopic Findings

	None Present	Present	
1. Crusting	0	1	
2. Erythema	0	1	
3. Swelling	0	1	
4. Scar Band	0	1	
5. Purulent Drainage	0	1	
6. Thick Mucous	0	1	
	None Present	Present in middle meatus	Present outside middle meatus
7. Polyps	0	1	2

Radiologic Examination

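### The ordered seven-level CGI response is compared between arms with a plain chi-square, which ignores the ordering and loses power for a shift that a rank-sum test would keep

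*Combined protocol and SAP*

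**What the plan says.** The CGI section, under the secondary outcome heading, introduces the measure: "The overall response to treatment will be measured with a modification of the Clinical Global Impression (CGI) scale". It is one patient-answered item scored 1 (very much improved) to 7 (very much worse), with no change at 4. On timing it says: "Upon completion of the study, subjects will be asked to answer the following question". The Calendar of Events also lists the scale at earlier visits; this point concerns the end-of-study response.

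The Statistical Analysis section has one sentence on it. It first tabulates: "The distribution of responses on the Clinical Global Impression (CGI) scale will be calculated within each intervention arm". It then tests: "the difference in responses between the two intervention arms will be compared for statistical significance with the chi-square statistic". The general threshold applies: "Statistical significance will be defined as a two-tailed test of significance p value of 0.05 or less".

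No trend, rank, exact or ordinal-model version is named for the CGI, and no rule for collapsing levels. The robust-regression fallback in the same section belongs to the general linear model for SNOT-22. On direction, the Statement of the Research Problem is explicit: "We anticipate that MF dispensed in a large volume, low-pressure device will be superior to that of MF nasal spray". No power is stated for the CGI: "The sample size for this study was calculated based on achieving a difference of 9 points or more on SNOT-22 scores".

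**The concern.** A Pearson chi-square gives the same p-value however the seven labels are rearranged. It does not use the fact that much improved is better than no change. With all seven levels occupied it spreads its sensitivity over six degrees of freedom, whereas the hypothesis of better overall response predicts movement in one direction along the scale. A rank-sum test puts its sensitivity there.

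At stake is the trial's only patient-rated overall response. In a trial of about 50 people, a non-significant chi-square could easily be misread as no difference when an ordinal test on the same data would have been more likely to show a shift. The planned analysis also gives no effect estimate that uses the ordering. By contrast, the SNOT-22 responder comparison, where a chi-square on two categories is natural, comes with a 95% confidence interval.

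**Working it through.** **The plan's own figure.** There is no CGI power or sample size to reproduce. The only sample-size figure concerns SNOT-22, and the check does not depend on it.

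**Inputs from the documents.** Seven ordered levels; two-sided 0.05; 25 per group (50 in all), or 22 per group from the 44 stated in Sample Size Calculations.

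**Assumptions.** The documents give no CGI distribution or effect. Four control-arm distributions were assumed, with proportional-odds shifts of odds ratio (OR) 2 to 6. A smaller size of 19 v 18 was added, from 44 × 0.85 = 37.4. This too is an assumption, because it is unclear whether 44 is before or after the 15% allowance.

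**Expected counts** (total ÷ number of cells):
- Seven levels: 50/14 = 3.6; 44/14 = 3.1; 37/14 = 2.6.
- Four levels: 50/8 = 6.25; 44/8 = 5.5; 37/8 = 4.6.

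The table is sparse, so type I error was checked as well as power.

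**Shift model.** With F(k) the proportion at level k or better, F₁/(1−F₁) = OR × F₀/(1−F₀). Example: if 30% of controls are at least much improved, the odds are 0.30/0.70 = 0.4286. At OR 3 they become 1.2857, so the proportion is 1.2857/2.2857 = 56%.

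**Tests compared.**
- Chi-square: Σ(O−E)²/E, with degrees of freedom equal to occupied levels minus 1.
- Rank-sum: z = (W − n₁(N+1)/2)/√V, where W is the sum of midranks in arm 1, V = (n₁n₂/12)[(N+1) − Σ(t³−t)/(N(N−1))], and t is the number at each level. No continuity correction; applying one changes power by at most 0.7 points.

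There were 20,000 simulated trials per setting (Monte Carlo standard error at most 0.4 points).

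**Type I error (OR 1).** Chi-square 2.9-3.4% with seven levels, rising to 4.9-5.1% with four; rank-sum 4.8-5.1%. Sparseness makes the chi-square conservative to near-nominal. It does not produce false positives.

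**Power at 22 per arm, OR 3:**

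| Levels in use | Assumed control distribution (%) | Chi-square | Rank-sum |
|---|---|---|---|
| 7 | 10/20/25/25/10/7/3 | 21.7% | 51.3% |
| 6 | 12/22/26/24/10/6 | 24.6% | 51.5% |
| 5 | 15/25/30/20/10 | 28.5% | 50.9% |
| 4 | 20/30/30/20 | 33.5% | 50.1% |

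Relative loss in the first row: 1 − 21.7/51.3 = 58%.

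**Relative loss at 22 per arm:**

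| OR | 7 levels | 6 | 5 | 4 |
|---|---|---|---|---|
| 2 | 65% | 58% | 47% | 37% |
| 3 | 58% | 52% | 44% | 33% |
| 4 | 50% | 43% | 36% | 26% |
| 6 | 33% | 28% | 23% | 16% |

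Over all three sample sizes the loss was 13-65% relative, or 7-35 percentage points. The rank-sum test was ahead in every setting.

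**Second set of distributions** (22 per arm, chi-square v rank-sum):

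| Assumed control distribution (%) | OR 2 | OR 3 | OR 4 | OR 5 |
|---|---|---|---|---|
| Flat over 7 levels | 10.5 v 24.8 | 23.0 v 52.4 | 37.3 v 71.4 | 49.8 v 83.0 |
| 8/17/30/30/8/5/2 | 9.1 v 24.5 | 21.5 v 51.1 | 36.1 v 70.1 | 49.6 v 82.5 |
| 5/20/35/30/6/3/1 | 8.9 v 23.5 | 22.2 v 50.1 | 37.7 v 69.5 | 50.9 v 80.8 |
| 10/25/35/30 (4 levels) | 14.8 v 23.6 | 32.6 v 49.6 | 51.0 v 69.9 | 64.8 v 82.0 |

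The direction is the same and the size similar.

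**Where the advantage disappears or reverses** (22 per arm):
- Benefit confined to a subset. From the first seven-level distribution, very much improved rises from 10% to 35%, minimally improved falls from 25% to 15%, and no change falls from 25% to 10%. Power is 33.5% (chi-square) v 33.9% (rank-sum).
- Pure difference in spread, 10/20/40/20/10% v 25/15/20/15/25%. Power is 36% v 6%.
- Only three levels in use (30/40/30%). The relative loss is 10-21%, or 5-11 points, for OR 2-6.

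**The case against.** The strongest reply is that the loss figures all assume a proportional-odds shift, the pattern that favours a rank test. A real benefit could be concentrated in a subset of responders, and then the two tests perform alike. If few levels are used the loss shrinks, so 13% is not a floor. The relative loss is largest at OR 2, where the rank-sum test itself has only 20-27% power and the comparison would be inconclusive either way. The CGI is secondary, the chi-square is valid, and the planned frequency table would let a reader see a shift.

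All of this stands as a limit on size. It does not rescue the choice of test. A concentrated benefit shows no gain from changing, not a harm. The pattern for which the chi-square is clearly better, a difference in spread without a shift, is not what the protocol hypothesises, and the retained table would display it.

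One could also read the chi-square as a trend version, but the text does not say so, and the same section uses the term for a percentage of responders.

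**Conclusion.** The concern holds. The planned CGI comparison discards the ordering of the scale and is less likely than an ordinal test to detect a consistent shift. With four to seven levels in use and OR 2-6, the relative loss is 13-65%; at 22 per arm and OR 3, power is 22-34% instead of about 50%.

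Confidence is high in what the text says and in the direction under a shift. The size depends on assumed distributions and odds ratios and on a proportional-odds pattern. The consequence is lost efficiency in one secondary comparison: there is no inflation of false positives and no effect on the primary SNOT-22 analysis. Nor would the change make the CGI comparison well powered for small effects. It is a worthwhile, inexpensive improvement.

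**What to change.** Replace the CGI test in Statistical Analysis with an ordinal one, fixed before unblinding. For example: *CGI responses at the end of the study will be compared between arms with a tie-corrected or exact Wilcoxon rank-sum test at two-sided 0.05; the frequency of each response will be tabulated by arm.* A proportional-odds model reporting the common odds ratio with its 95% confidence interval serves equally well and adds an effect estimate. If a trend form of the chi-square was intended, the plan should name it.

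The cost is one sentence and no new data. The downside is less sensitivity to differences without a shift, such as the spread example above; keeping the table by arm leaves such a pattern visible.
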